#### 5.1 Planned Duration of Protocol

Stage 1 will take up to six months (full dose group) or four months (medium and low dose groups) to complete after screening and baseline evaluation. The screening and baseline evaluation can take up to 4 months. In addition, if the length of time between the end of tapering and the first experimental session is longer than a month, the CAPS should be repeated to show consistency between this score and the baseline CAPS. The open-label study segment for participants initially assigned to receive low dose or medium-dose MDMA (Stage 2) will last an additional five months from the single introductory and review psychotherapy session until the evaluation two months after the final open-label MDMA-assisted psychotherapy session. The time period between the end of Stage 1 and the start of Stage 2 should not exceed 5 months for any participant with CAPS re-assessment done if there is an interval of greater than 8 weeks between the end of Stage 1 and the beginning of Stage 2. The 12-month follow-up will occur a year after the final experimental session for all participants who complete Stage 1 only, and a year after the final open-label session for any participants who enroll in and complete

Stage 2. For each participant who enrolls only in Stage 1, the entire study duration will be up to 1.5 years including the 12-month long-term follow-up, and for the participants that complete both Stage 1 and Stage 2 follow-ups, the study may take about two years.

## 5.2 Randomization and Subject Numbering

This is a randomized, triple-blind, dose comparison study with an open-label cross-over segment. For Stage 1, a randomization list will be prepared at the beginning of the study. Another list will be created to replace subjects who withdraw from the study and are unblinded. Each participant will be assigned to one of the three dose conditions; 30 mg (low dose), 75 mg (medium-dose) or 125 mg (full dose). Twelve participants will be assigned to the full-dose condition, six participants to the 75 mg condition and six participants to the 30 mg low dose condition. The study will employ a blinded randomization procedure that will maintain the 2:1:1 ratio while maintaining the blind and ensuring that each subsequent condition assignment is not predicated on the previous assignment. Drug containers will be assigned a unique random number. At least 24 hours before each experimental session, container assignments to each subject will be performed on a per experimental session basis, and the container will contain the initial and supplemental capsules for a single experimental session. This will be done by contacting the Randomization Monitor or logging into the web-based randomization system. The unblinded Randomization Monitor will also oversee drug encapsulation and labeling of drug bottles. Replacement doses for subjects who replace dropouts that retain the same ratio of condition assignment will also be created. The Randomization Monitor will provide the investigators with sealed envelopes that will permit emergency unblinding for an individual subject if required. In all other cases, the blind will be maintained up through the primary endpoint assessment. The participant, independent rater and both investigators conducting psychotherapy will be blind to condition assignment, until that point. Participants who drop out of the study or are withdrawn by the Clinical Investigator prior to the primary endpoint will be replaced until blinded data has been collected from 24 participants. Subjects who withdraw during Stage 2 or during the long-term follow-up portion of the study will not be replaced.

Prior to enrollment, subjects will be tracked with their initials and a screening number assigned sequentially starting at "001". Subjects who meet the study admission criteria will be enrolled into the study and will be assigned a 4-digit subject number. The first two digits identify the study number (08). The next two digits identify the subject within the site and will be assigned sequentially, with 01 corresponding to the first subject enrolled, e.g. the first subject enrolled in study number 08 will be 0801, second 0802, etc.

### 5.3 Recruitment and Subject Population

Candidates for participation will be 24 veterans, firefighters or police officers with chronic, treatment-resistant, PTSD arising from their service. Treatment resistance is defined as PTSD of at least six months duration where patients were unable to achieve remission despite having received prior treatment with either pharmacotherapy or psychotherapy of adequate dose/duration or who discontinued treatment due to lack of

tolerability. Of the 24 subjects to be enrolled in this study, at least 18 must have PTSD of less than 10 years duration (from Iraq and Afghanistan Wars) while up to 6 may have PTSD of more than 10 years (including the Vietnam War). A subject would not be excluded for having more than one traumatic event, but would be excluded if a traumatic event not related to military, fire or police service was the major contributor to the PTSD symptoms. Participants must be at least 18 years old with a diagnosis of PTSD and a screening CAPS score equal to or greater than 50 at baseline evaluation. Ideally, subjects will include twelve men and twelve women. Subjects of each sex who qualify and agree to participate will be accepted into the study in chronological order until twelve subjects of either sex have been enrolled. Enrollment will then be limited to members of the opposite sex until twelve male and twelve female subjects have been enrolled. If, however, attempts to recruit equal numbers of male and female subjects turns out to result in undue delay in proceeding with the study, the investigators may, after discussion with the sponsor, revert to enrolling subjects of either sex in order to reach the goal of 24 participants.

Participants will be recruited via letters of referral sent to psychiatrists and psychotherapists, contact with veterans' organizations, written advertisements, announcements placed on appropriate internet sites and the sponsor website, and word of mouth. Candidates may also be individuals who had previously contacted the investigators expressing interest in taking part in the initial study of MDMA-assisted psychotherapy for PTSD after that study had closed enrollment.

One of the investigators or their assistant will interview prospective participants by telephone to learn if they meet basic eligibility criteria. If the prospective participant is interested in taking part in the study, the investigators will provide her or him with consent materials for review and consideration through postal mail or electronically. If, after review, a potential participant remains interested in taking part in the study, then he or she will meet with the investigators to complete the consent process. Participants will complete a quiz to assess their understanding of the consent forms. Investigators will then review the quiz responses with the prospective participant to ensure that he or she correctly understands study procedures, risks and benefits.

#### 5.3.1 Inclusion Criteria

Individuals eligible to be enrolled into this protocol are participants who:

- 1. Meet DSM IV criteria for current PTSD with a duration of 6 months or longer resulting from traumatic experience during military service;
- 2. Have a CAPS score of 50 or higher, indicating moderate to severe PTSD symptoms;
- 3. Have had at least one unsuccessful attempt at treatment for PTSD with medication, such as an SSRI, SNRI, or mirtazapine, or one unsuccessful treatment with any form of psychotherapy for which there exists a controlled trial indicating efficacy in the treatment of PTSD. This includes cognitive-behavioral therapy

(including exposure therapy), stress inoculation training, including anxiety management, insight-oriented psychotherapy, and EMDR.

OR who discontinued treatment due to either:

- Inability to tolerate psychotherapy for PTSD (e.g. persistent "overengagement" when attempting Prolonged Exposure Therapy) or
- Inability to tolerate psychopharmacology for PTSD due to treatment-emergent side effects;

Treatment will be deemed to have been unsuccessful if the participant continues to meet criteria for current PTSD following the treatment.

- 4. Are at least 18 years old;
- 5. If in ongoing psychotherapy at the time subjects are recruited into the study, participants may continue to see their outside therapist during the course of the study. Participants must sign a release for the investigators to communicate directly with their therapist. Subjects may not change therapists, increase the frequency of therapy or commence any new type of therapy until after the evaluation session 2 months after the final experimental session. Subjects who do not live within reasonable driving distance of the study site (equal to or less than an estimated two hours' drive from the study site) must have a therapist in the area in which they live whom they can call on for support and evaluation if necessary;
- 6. Are willing to refrain from taking any psychiatric medications during the study period, with the exception of gabapentin when prescribed for pain control. If the subject is on stimulants for ADHD at baseline, they can continue to use them at the same dose and frequency as long as they discontinue 5 half lives before each MDMA session and do not restart for 10 days after each MDMA administration. Any psychoactive drugs, including stimulants, will be tapered in an appropriate fashion to avoid withdrawal effects. Medications will only be discontinued after consultation with the prescribing physician;
- 7. Agree that, for one week preceding the MDMA session will refrain from:
  - a. taking any herbal supplement (except with prior approval of the research team);
  - b. taking any nonprescription medications (with the exception of nonsteroidal anti-inflammatory drugs or acetaminophen unless with prior approval of the research team);
  - taking any prescription medications, with the exception of birth control pills, thyroid hormones or other medications approved by the research team);
- 8. Agree to take nothing by mouth except alcohol-free liquids after 12:00 A.M. (midnight) the evening before the experimental session;
- 9. Refrain from the use of any psychoactive drug, with the exception of caffeine or nicotine, within 24 hours of each MDMA session;
- 10. Agree not to use caffeine or nicotine for 2 hours before and 6 hours after the dose of MDMA;
- 11. Are willing to remain overnight at the study site;

12. Agree to have transportation other than driving themselves home or to where the participants are staying after the integrative session on the day after the MDMA session;

22 of 79

- 13. Are willing to be contacted via telephone for all necessary telephone contacts;
- 14. Must have a negative pregnancy test if able to bear children, and agree to use an effective form of birth control;
- 15. Must provide a contact (relative, spouse, close friend or other caregiver) who is willing and able to be reached by the investigators in the event of a participant becoming suicidal;
- 16. Must agree to inform the investigators within 48 hours of any medical conditions and procedures;
- 17. Are proficient in speaking and reading English;
- 18. Agree to have all clinic visit sessions recorded to audio and video;
- 19. Agree to not participate in any other interventional clinical trials during the duration of this study.

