## 2.0 Background Information

#### 2.1 Introduction

The Multidisciplinary Association for Psychedelic Studies (MAPS) is a non-profit research and educational organization working to obtain approval for the prescription use of 3,4-methylenedioxymethamphetamine (MDMA)-assisted psychotherapy in patients with posttraumatic stress disorder (PTSD).

Encouraging data has been obtained and submitted to the FDA from MAPS' recently completed United States (U.S.) pilot study, IND #63-384 (MP1). MAPS is currently sponsoring another Phase 2 study in Switzerland. An additional Phase 2 study is planned to start in the near future in Canada, with approval from Health Canada and a Canadian Institutional Review Board (IRB) already obtained. Ongoing and planned Phase 2 studies, along with the study described in this protocol, are laying the groundwork for an eventual End-of-Phase 2 meeting with FDA and possible Phase 3 multi-site MDMA/PTSD research studies.

The proposed pilot study will examine the safety and efficacy of MDMA-assisted psychotherapy in twenty-four veterans, firefighters or police officers with service related PTSD, and will seek to enroll roughly equal numbers of men and women. This study will include those with chronic PTSD of at least six months duration who satisfy PTSD diagnostic criteria despite having received prior treatment with either medication or psychotherapy. Full, medium and low dose MDMA will be assessed in Stage 1, as well as the benefit of three vs. two full dose sessions. Subjects who received the medium and low dose during Stage 1 will have the opportunity to cross over and take part in a second study segment, referred to as Stage 2, with three open-label experimental sessions. Stage 2 will be used to explore the optimal therapeutic dose of MDMA using a clinical titration dosing strategy.

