### 5.0 Protocol Design

This randomized, triple-blind study will examine the safety and efficacy of MDMA-assisted psychotherapy with 30, 75 or 125 mg MDMA in twenty-four veterans, firefighters and police officers diagnosed with chronic, treatment-resistant PTSD arising from their service. These participants will ideally, but not necessarily, include twelve men and twelve women. Supplemental doses of half the initial dose may be administered between 1.5 and 2.5 hours after the initial dose was administered.

Prior to undergoing the first MDMA-assisted (experimental) session, all participants will undergo three 90-minute preparatory non-drug psychotherapy sessions with a male and female co-therapist team. Stage 1 of the study will consist of two blinded experimental sessions and, for the full dose group, one open-label experimental session, each lasting six to eight hours and scheduled three to five weeks apart. The study will be unblinded after the second experimental session in Stage 1, which constitutes the primary endpoint assessment. After unblinding, medium dose and low dose subjects will have the opportunity to continue to open-label Stage 2, unless they meet any exclusion criteria for study participation and full dose subjects will complete the third open-label experimental session. All subjects will complete a long-term follow-up visit 12 months after their final experimental session. All psychotherapy sessions may be recorded to audio and video. In the first open-label experimental session in Stage 2, subjects will receive 100mg with an optional supplemental dose of 50mg. In the second and third open-label experimental session in Stage 2, subjects will receive one of two active doses of MDMA that are clinically titrated by the CI. Experimental sessions will otherwise follow the same sequence of events after a single preparatory session. (See Time and Events Table).

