Visit #	Pre-Study	V1	V 2,3,4	V5	V 6,7,8	V9	V 10,11,12	V13	V14	V 15,16,17	V18	
Type of Visit	Screening may take place over more than one day		Preparatory Sessions	Experimental Session 1	Integrative Sessions	Experimental Session 2	Integrative Sessions	Primary Endpoint	Experimental Session 3	Integrative Sessions	End of Stage 1 & Outcome	
Visit Timing or Study day or Window	Up to 2 months prior to Visit 1		Prior to V5 M	Up to 7 weeks post V1	Before V9 A	3-5 weeks post V5	Before V13 A	1 month post V9	3-5 weeks post V9 N	Before V18 A, N	May happen over > 1 day. 2 mo. post V14 N	
Initial Phone Screen	X											
Informed Consent	X											
Medical/Psychiatric History	X											
General Phys. Exam (BP, Pulse, Temp)	X											
Brief Neurological Exam	X											
ECG	X											
SCID-I-RV	X											
Clinical Lab Tests, w/ HIV, HCV test	X											
Collect Concomitant Medication	X	X	X	X	X	X	X	X	X	X	X	
Medication Taper (if applicable)	X	X										
Study Enrollment after meeting I/E		X										
Record to Audio/Video	$X^{L}$		X	X	X	X	X	$X^{L}$	X	X	$X^{L}$	
General Well-Being		X	X	X	X	X	X		X	X		
Drug Screen	X			X		X			X			
Pregnancy Screen (if applicable)	X			X		X			X			
Complete Randomization Procedure				X B								
CAPS, GAF, BDI-II, PTGI, PSQI, DES-II (IR)	X							X			X	
NEO PI (Ind. Rater)	X			CDE	I	CDE	1	X	CDE	1		
C-SSRS		X	X	$X^{C,D,E}$	X I	$X^{C,D,E}$	$X^{I}$	X	$X^{C,D,E}$	$X^{I}$	X	
Administer IP Drug + Therapy, SOCQ				X		X			X			
Monitoring of BP, Pulse and Temp.				X		X			X			
SUD				$X^{F,E}$		$X^{F,E}$			$X^{F,E}$			
Beliefs of Condition Assignment					$X^{K}$		$X^{K}$			$X^{K}$		
Overnight Stay				X		X			X			
Integrative Therapy Session					X		X			X		
7 days Integrative Telephone Contact					Χ I		XI			X I		
AEs Requiring Medical Attention				X	X	X	X	X	X	X	X	
Spont. Reported Reactions and all AEs				X	X	X	X		X	X		
Changes in Tinnitus and/or Pain	X O		X E, O	X E, O	X E, O	X E, O	X E, O	$\chi^{O}$	X E, O	X E, O	$\chi^{O}$	
AEs of psychiatric status or withdrawal		X	X	X	X	X	X	X	X	X	X	
Serious Adverse Events		X	X	X	X	X	X	X	X	X	X	
Issue Memory Aid Card H											X	
Unblinding J								X				
Perception of Third Session								$X^N$			$X^{N}$	
RRPQ											X H	

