A =First Integrative session is 1 day after exp session B = At least 24 hrs prior to 1st exp. session C =Approximately 6 hours post MDMA D =At the beginning of the session E =As needed F=Approximately every 60 minutes G =Given on 2nd preparatory session after meds are tapered (V3) H = Only for subjects starting Long term Follow up and not going to Stage 2 I =For 7 days post Exp. Session, C-SSRS D2 and D7 of calls only, General well being for all 7 days J =Subjects in the medium or low dose group will not have visits 14-18, but will instead move onto Stage 2. K= On the day of the 1st integrative session following the Exp. Session I =CAPS may be videotaned M=First preparatory session (V2) may happen at the time of screening, before enrollment. N= Full dose subjects only. O= Only in subjects with pre-existing timitus and/or chronic pain

Table4.Stage2Time&Events	Preparatory	Experiment	tal Session 1	on 1 Experimental Session 2			Experimen	tal Session 3	Follow-Up		Long Term Follow-Up
Visit #	V19*	V20	V 21,22,23	V24	V 25,26,27	V28	V29	V 30,31,32	V33		1 Year Follow-up
Type of Visit	Preparatory Session	Experimental Session 1	Integrative Sessions	Experimenta 1 Session 2	Integrative Sessions	Secondary endpoint	Experiment al Session 3	Integrative Sessions	End of Stage 2 & Outcome		Follow-Up & Outcome
Visit Timing or Study day or Window	Within maximum of 5 months of V13*	After V19	Before V24 A	3-5 weeks post V20	Before V28 A	1 month post V24, beforeV29	3-5 weeks post V24	Before V33	May happen over > 1 day 2 months post V29		May happen over > 1 day. One Year post V14 or V29
Confirm Informed Consent	X										
Confirm Inclusion/Exclusion	X										
Enrollment in Stage 2	X										
Collect Concomitant Medication	X	X	X	X	X	X	X	X	X	7	X
Record to Audio/Video	X	X	X	X	X	$X^{H}$	X	X	$X^{H}$	Stage	
General Well-Being	X	X	X	X	X		X	X	X	Sta	
Drug Screen		X		X			X			or ,	
Pregnancy Screen (if applicable)		X		X			X			_	
CAPS, GAF, BDI-II, PTGI, PSQI, DES-II (IR)	Use V13*					X			X	Stage	X
NEO PI with Ind. Rater	Use V13*								X	er	X
C-SSRS	X	X C, D, E	$X^{G}$	X C, D, E	X G		X C, D, E	X G	X	after	X
Administer IP Drug + Therapy, SOCQ		X		X			X			dn	
Monitoring of BP, Pulse and Temp.		X		X			X			Follow	
SUD		X D, F		X D, F			X D, F			o	
Overnight Stay		X		X			X				
Integrative Therapy Session			X		X			X		Term	
7 days Integrative Telephone Contact			X G		X G			X G		Ī,	

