## **6.0 Sample Size and Power Considerations**

This study is a pilot investigation intended to gather preliminary data on the safety and efficacy of MDMA in 24 evaluable veterans, firefighters, or police officers with chronic, treatment-resistant PTSD. Because of their exploratory nature, pilot studies are often not powered for detecting the desired effect. Because it is a pilot study in a small sample, results will be used to collect effect size estimates for statistical power calculations for adequately powered subsequent studies.

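### Inclusion criterion 1 admits only trauma from military service, contradicting Section 5.3 and the stated population, which also cover fire and police service

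*Protocol*

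**What the plan says.** Criterion 1 in Protocol 5.3.1 requires that participants "Meet DSM IV criteria for current PTSD with a duration of 6 months or longer resulting from traumatic experience during military service". It offers no alternative source of trauma.

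Section 5.3, of which 5.3.1 is a subsection, has its own rule on trauma source: a person "would be excluded if a traumatic event not related to military, fire or police service was the major contributor to the PTSD symptoms". It also sets a quota by duration of illness, under which "at least 18 must have PTSD of less than 10 years duration (from Iraq and Afghanistan Wars"), while up to 6 may have PTSD of longer than 10 years, with the Vietnam War given as an included case.

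The population is described the same way throughout. Protocol 2.1 places the study "in twenty-four veterans, firefighters or police officers with service related PTSD". Protocol 3.0 and 5.0 name the same three occupations, as do SAP 2.0 and 4.0. SAP 6.0 refers to "24 evaluable veterans, firefighters, or police officers with chronic, treatment-resistant PTSD".

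On enrolment, Protocol Table 3 (Stage 1 Time and Events) has this entry at visit 1: "Study Enrollment after meeting I/E".

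**The concern.** Criterion 1 turns on where the trauma arose, not on occupation. Two of the three named groups can therefore satisfy it only if their PTSD came from military service. The site is left with two unattractive courses. It can apply the list and screen out people whom the trial says it studies, or it can follow the evident intent and enrol them against a written criterion.

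The second course leaves a mark in the analysis. SAP 8.3 has a deviation category for subjects who entered without meeting criteria, and the categories are summarised by MDMA group. A subject from the intended population would then be reported as wrongly enrolled.

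**Working it through.** The clash is one of wording, so the check is to set the rules side by side.

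**Step 1. Apply both rules to the same cases.**

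| Case | Criterion 1 (5.3.1) | Trauma-source rule (5.3) |
|---|---|---|
| Veteran, PTSD from military service | met | not excluded |
| Firefighter or police officer, PTSD from military service | met | not excluded |
| Firefighter or police officer, PTSD only from fire or police service | **not met** | not excluded |

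The rules part in the third row, and that row is part of the population described in Protocol 2.1, 5.0 and 5.3.

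**Step 2. Look for text that widens criterion 1.** None of the other 18 inclusion criteria or the 14 exclusion criteria in 5.3.1 and 5.3.2 adds fire or police service, or limits criterion 1 to veterans. The SAP has no separate eligibility list. Both conflicting texts are current.

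**Step 3. Ask which text a site would act on.** The opening line of 5.3.1 presents the list as defining who may be enrolled. Protocol 5.2 says that subjects who meet the admission criteria will be enrolled, and Table 3 ties enrolment to the inclusion and exclusion criteria.

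**Step 4. Check the quota in 5.3.** Two readings are possible.

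- If the mention of Iraq and Afghanistan is a condition, 18/24 = 75% or more of the places are tied to those wars. At most 24 − 18 = 6 places (6/24 = 25%) remain for any other service trauma.
- If the wars are only examples, the quota concerns duration alone and sets no such limit.

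The text does not settle which is meant. Only this parenthesis could restrict. The one on the Vietnam War is introduced as an inclusion, so it is not exhaustive.

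**Step 5. Trace the analysis consequence.** SAP 8.1 defines ITT as everyone randomised and Safety as everyone treated, so an affected subject stays in ITT once randomised and in Safety once treated. The deviation category in SAP 8.3 applies on its face. The major-deviation definition in the same section does include people found not to meet the criteria in the course of the study. Its other limb, however, literally makes everyone who completed through the primary endpoint a major deviation, which contradicts the per-protocol definition in SAP 8.1. No firm conclusion on per-protocol membership can be drawn from it.

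**The case against.** The best defence is that the intent is not in doubt. Section 5.3 is the parent of 5.3.1 and holds operative rules that appear nowhere else: the duration quota, the balance by sex and the exclusion by trauma source. Protocol 6.0 has the investigators decide on enrolment after reviewing all the information. Every description of the population names the same three groups. On this view a phrase is missing from one line, and a sensible site would read it in.

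Much of that stands, and it lowers the risk that anyone is wrongly turned away. It does not remove the defect. The trauma-source rule in 5.3 is a bar. Passing it does not satisfy criterion 1, and when both are applied together only military trauma gets through. A site that reads in the missing phrase is departing from the written list.

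A reader might go further in three ways that the documents do not support.

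- *That affected subjects will be dropped from the per-protocol set.* The faulty definition in SAP 8.3 cannot show this. If it did apply, it would apply in all three arms. SAP 8.9.1 also names no analysis population for the primary ANOVA, so no effect on the primary result is shown.
- *That classification could be settled with dose known, because each subject is unblinded at visit 13.* Trauma source would ordinarily be known from the screening history and interviews, and nothing suggests that the decision would wait until then.
- *That the problem recurs at Stage 2.* Section 5.0 says that low- and medium-dose subjects "will have the opportunity to continue to open-label Stage 2, unless they meet any exclusion criteria for study participation", whereas Table 4 has "Confirm Inclusion/Exclusion" at visit 19. That mismatch concerns all the inclusion criteria and would exist if criterion 1 were perfectly worded. It is a separate matter.

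**Conclusion.** The point holds as a contradiction in an operative eligibility rule. Criterion 1 is wrong as written against Section 5.3 and against the population named throughout both documents. Confidence in the wording clash is high, since it rests on current text and on no assumption.

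Its practical size cannot be stated. The documents do not say how many of the 24 have PTSD from fire or police service, and the number may be zero. One subject is 1/6 = 16.7% of the low- or medium-dose arm and 1/12 = 8.3% of the full-dose arm, but that is true of any subject and does not measure this defect. The 75% and 25% shares under the quota hold only if its mention of the two wars is read as a condition.

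The supported consequences are that eligible-by-intent candidates may be screened out, or enrolled and then listed as deviations. This should be corrected, but it does not by itself threaten the planned comparison.

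**What to change.** 1. Amend criterion 1 so that the qualifying trauma may arise during military, fire or police service, using the scope that Section 5.3 already has. This creates no new eligibility rule.
2. In the same amendment, state that the mention of the Iraq and Afghanistan wars in the duration quota does not bar fire or police service trauma from those places, or otherwise reconcile it with the stated population.

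The cost is one short protocol amendment with IRB approval. Visits, measures, sample size and planned tests do not change.
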